## 8 Research Question and Objectives

The primary objectives of the DUS are as follows:

- To describe the characteristics of new users of cilostazol according to the following factors:
  - Demographics (e.g., age and sex)
  - Baseline comorbidity including conditions listed in the SmPC and the risk management plan (RMP) as potential or identified safety concerns (Otsuka Pharmaceutical Europe Ltd, 2012).
  - Baseline and concurrent use of medications potentially interacting with cilostazol and other medications

- Specific comorbidity and use of medications considered in the proposed risk minimisation measures, specifically those included in the proposed changes to the SmPC
- To describe the duration of the use of cilostazol and discontinuation patterns

Secondary objectives of the DUS are as follows:

- To quantify and describe off-label prescribing
- To describe dosage patterns of the use of cilostazol
- To assess the proportion of patients who are hospitalised for any cause while treated with cilostazol
- To describe the medical specialties of physicians prescribing cilostazol

The study objectives are the same for DUS1 and DUS2. DUS1 provides the baseline characteristics of users of cilostazol before the implementation of SmPC changes and communication with HCPs. DUS2 will be conducted after the implementation of these measures to evaluate their impact on the prescribing of cilostazol.

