### 9.2.2.1 Study Period for DUS2

The study period for DUS 2 is from 1 January 2014 to 31 December 2014, following the implementation of changes to the summary of product characteristics (SmPC) and communication activities with HCPs that took place during 2013 (Figure 2).

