#### **9.2.5 Exclusion Criteria**

Because the DUS seeks to characterise all new users of cilostazol, no exclusion criteria regarding age, sex, or comorbidity will be applied.

Patients who have their first recorded prescription for cilostazol during the eligibility period (6 months of continuous enrolment in the database) will be excluded as they will not be new users at the start date. In addition, for DUS2, patients who have a recorded prescription for cilostazol at any time before the start will also be excluded.

Patients with records flagged as incomplete or as substandard data quality according to each database-specific quality-control measures will be excluded.

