#### **9.2.6 Follow-up**

Each member of the study cohort will be followed from the start date until the first of the following termination dates:

- End of enrolment in the database
- Death
- End of study period (for DUS2, 31 December 2014)

For each member of the study cohort, comorbidity will be assessed for the entire period of data availability before the start date.

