### **9.3.6 Baseline Characterisation of New Users for the Assessment of Planned Risk Minimisation Measures (SmPC Changes)**

New users of cilostazol will be characterised to evaluate the impact of the risk minimisation measures that Otsuka submitted to the EMA in October 2012. The risk minimisation measures include SmPC changes to identify a more restricted target population and to decrease the daily dose when cilostazol is used with potentially interacting medications. The risk minimisation measures also include communication initiatives to HCPs.

To evaluate the impact of the risk minimisation measures, a second DUS (DUS2) will be initiated 6 months after the implementation of the SmPC changes, and results will be compared with those obtained in the first DUS (DUS1).

The SmPC changes and the characteristics of users that will be evaluated in DUS1 and DUS2 are detailed in Table 7.

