### 9.7.1 Number of Users and Patterns of Use

Analysis Tables 1, 2, and 29: Use of cilostazol during the study period. Number of users; number of prescriptions; number of packages; total number of DDDs; mean number and standard deviation (SD) of packages and DDDs per prescription; and mean (SD) number of prescriptions, packages, and DDDs per user. Analyses will be stratified by year of start of cilostazol (DUS1 only) and formulation: 50 mg and 100 mg (Analysis Table 1), and by formulation and package size (Analysis Table 2). The number and percentage of users by the number of prescriptions received during follow-up will be calculated (Analysis Table 29). The number of users of cilostazol with less than 12 months of continuous enrolment in the database will also be ascertained (Analysis Table 1A).

Analysis Tables 3 and 30: Distribution of users at the start date. Number of users, number of prescriptions, number of packages, number of DDDs, mean (SD) number of packages per user, and mean (SD) number of DDDs per user will be ascertained at the start date for each combination of formulation and package size. The distribution of users by year of start date will be generated (DUS1 only) (Analysis Table 30).

Analysis Tables 4, 25, and 31: Age and sex distribution of users at the start date. The number and percentage of users at the start date will be described by sex and the following groups of age (in years): (1) < 18, 18-29, 30-39, 40-49, 50-59, 60-69, 70-79, ≥ 80 and (2) < 70 and ≥ 70 (Analysis Table 4). Age- and sex-specific prevalence of users of cilostazol during the study period will be calculated (Analysis Table 25). For DUS2, prevalence of use will be calculated as the proportion of patients from the source population who received at least one prescription for cilostazol during 2014 (includes new users and prevalent users). In addition, the mean (SD) of age by sex among cilostazol users at first use will be calculated (Analysis Table 31).

Analysis Table 5: Daily dose at the start date. Daily dose prescribed at the start date will be calculated using the recorded information on strength and quantity prescribed and the days of supply of the first prescription for cilostazol. The daily dose prescribed at the start date will be described by sex and age group (< 70 years, ≥ 70 years).

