Analysis Table 6: Person-years of use. Person-years of use will be accumulated for each user of cilostazol and across all users. Person-years of use will be described by sex and age (< 70 years, ≥ 70 years). The mean (SD), median, 25th percentile, and 75th percentile (P75) of person-years will be calculated by sex and age group (< 70 years, ≥ 70 years).

Analysis Table 7: Duration of continuous use. Duration of use refers to the duration of continuous treatment with cilostazol. Duration will be ascertained by the total number of days of supply of consecutive prescriptions, defined as those prescribed with a maximum interval of 60 days between dates of consecutive prescriptions. Sensitivity analyses will be conducted for a maximum interval of 90 days between dates of consecutive prescriptions. Person-years of consecutive use will be accumulated for each user of cilostazol and across all users. Person-years of consecutive use will be described by sex and age group (< 70 years, ≥ 70 years). The mean (SD), median, 25th percentile, and 75th percentile of person-years of consecutive use will be calculated by sex and age group (< 70 years, ≥ 70 years).

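### Analysis Table 7 summarises duration of continuous use by raw means and medians without censoring, so DUS2 would look shorter than DUS1 even if behaviour did not change

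*Protocol*

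**What the plan says.** Protocol section 8 lists as a primary objective "To describe the duration of the use of cilostazol and discontinuation patterns" and adds "The study objectives are the same for DUS1 and DUS2", with DUS1 as the baseline for DUS2.

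Section 9.7.1 fixes how duration is reported. Analysis Table 7 accumulates person-years over consecutive prescriptions with gaps of up to 60 days (90 days in a sensitivity analysis). Then: "The mean (SD), median, 25th percentile, and 75th percentile of person-years of consecutive use will be calculated by sex and age group". Nothing is said about treatment that is still running when data end.

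The DUS2 window is short and closes for entry and follow-up on the same day. Section 9.2.2.1: "The study period for DUS 2 is from 1 January 2014 to 31 December 2014". Section 9.2.6 lists as a termination date "End of study period (for DUS2, 31 December 2014". Section 9.2.5 adds that "for DUS2, patients who have a recorded prescription for cilostazol at any time before the start will also be excluded", so nobody brings in treatment time from before 2014. Protocol Table 2 gives much longer DUS1 windows.

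Elsewhere the protocol does allow for censoring. Section 9.7.5 evaluates discontinuation between 3 and 4 months by Kaplan-Meier (Analysis Tables 17A and 26), and the amendment log gives censoring as the reason.

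**The concern.** A raw mean or median of observed time counts a user who is still on treatment at the end of data as one who stopped that day. The result is too short, and the error depends on the length of the window, which differs between phases and between databases. In DUS2 a user who starts in December 2014 can contribute at most one month.

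Section 9.3.6 says of DUS2 that "results will be compared with those obtained in the first DUS (DUS1". Once the two Table 7 results stand side by side, a fall in duration will appear that is partly or wholly produced by the calendar. The DUS1 durations are not comparable across countries either, because their windows differ about fivefold. The 60- and 90-day analyses do not help: they concern gaps between prescriptions, not the end of data.

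**Working it through.** **Inputs from the Protocol.** Windows, counted in whole months from Table 2 and section 9.2.2.1: IACS 24, SIDIAP 35, Sweden 45, GePaRD 60, THIN 127, DUS2 12.

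**Inputs assumed.** The Protocol gives no persistence figure. I take true duration T as exponential with a median of 3, 6 or 12 months, the same in both phases. Entry is even over the window, so available follow-up U is uniform on (0, L). There are no deaths or disenrolments. Mean available follow-up is L/2: 6 months in DUS2, and 12 to 63.5 months in DUS1.

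**Formulas.** The observed duration is min(T, U). With λ = ln 2 / true median:

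- Proportion cut off by end of data: p = (1 − e^(−λL)) / (λL)
- Raw mean: (1/λ)(1 − p)
- Raw median m: solves e^(−λm)(1 − m/L) = 0.5

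**One case in full: true median 6, DUS2.** λ = 0.1155 and λL = 1.386, so p = (1 − 0.25)/1.386 = 0.541. The raw mean is 8.656 × (1 − 0.541) = 3.97 months. At m = 3.26, 0.686 × 0.728 = 0.500, so the raw median is 3.3 months. For IACS, L = 24 gives p = 0.338 and a raw mean of 8.656 × 0.662 = 5.73 months. The DUS2 mean is then 1 − 3.97/5.73 = 31% shorter with identical behaviour.

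**All cases (months).**

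| True median | DUS2 cut off | Raw median DUS2 | Raw median DUS1, IACS to THIN | Raw mean DUS2 | Raw mean DUS1, IACS to THIN | DUS2 mean shorter by |
|---|---|---|---|---|---|---|
| 3 | 34% | 2.1 | 2.5-2.9 | 2.86 | 3.55-4.18 | 19-31% |
| 6 | 54% | 3.3 | 4.3-5.6 | 3.97 | 5.73-8.07 | 31-51% |
| 12 | 72% | 4.3 | 6.5-10.5 | 4.82 | 7.95-14.95 | 39-68% |

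A simulation of 1,000,000 users per scenario gives the same medians and cut-off proportions. SIDIAP, Sweden and GePaRD fall between IACS and THIN.

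**Other duration shape.** With a Weibull shape of 0.7 (many early stoppers), raw medians for true medians of 3, 6 and 12 months are 2.0, 2.9 and 3.8 in DUS2. In DUS1 they are 2.4-2.9, 3.9-5.5 and 5.8-10.0. The pattern is the same.

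**Does censoring repair it?** Applying Kaplan-Meier to the simulated exponential data gives, for a true median of 6 months, a median of 6.0 and 6-month persistence of 0.50 in DUS2 and in every DUS1 window. For a true median of 12 months, the DUS2 median lies at the edge of its window and is not reached, but 6-month persistence is 0.71 in both phases.

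**The case against.** The strongest reply is that this is a descriptive study and that the question raised by the SmPC change is answered elsewhere. Section 9.3.6 makes discontinuation between 3 and 4 months, estimated by Kaplan-Meier, the proxy for lack of efficacy. Mean or median duration is not among the characteristics listed there, and no section plans a formal DUS1-DUS2 contrast of Table 7. That stands. A reader might infer that a shorter DUS2 duration would be reported as proof that the label change worked, but the Protocol does not assign that conclusion to Table 7. The comparison of durations follows only from the shared objective and the baseline role of DUS1.

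A reader might also extend the criticism to Analysis Tables 1, 6 and 29. For Table 29, section 9.7.1 says: "The number and percentage of users by the number of prescriptions received during follow-up will be calculated (Analysis Table 29". Tables 1 and 6 likewise describe use during the study period. They do not claim to estimate complete treatment duration, so they need a caution rather than a new method.

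Finally, a reader might try to size the effect from the Swedish counts in Protocol Table 10. They do not support it. The number of unique users, 1,800 to 2,200, is itself an estimate, and a calendar year with any use is not continuous use under a 60-day gap. A simple exponential model with even entry also does not reproduce those counts.

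None of this rescues Table 7. It is the stated answer to the duration half of a primary objective, and its estimator is biased in each phase taken alone.

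**Conclusion.** The point holds for Analysis Table 7. Raw summaries understate duration of continuous use in every database, and most in DUS2. With unchanged behaviour, the DUS2 raw mean would be about 19% to 68% shorter than in DUS1 across true medians of 3 to 12 months and windows from IACS to THIN.

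The size rests on assumed persistence, even entry and no loss to death or disenrolment. It also takes observed use as ending with follow-up: if the last prescription's supply were counted in full, the 12-month limit could be passed by that supply, which would not remove the bias.

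A reader might infer that DUS2 durations must come out far shorter whatever patients do. That goes too far. With short use and the IACS window the gap is modest, and if DUS1 use were very short while DUS2 users rarely stopped, the DUS2 raw mean (up to about 6 months) could exceed that of DUS1. The supported statement is that DUS2 would appear shorter even if nothing changed.

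**What to change.** **Table 7.** Estimate time on continuous treatment by Kaplan-Meier, censored at end of enrolment, death or end of study period. Report the median and quartiles where reached. For any comparison between DUS1 and DUS2, or between databases, use persistence and restricted mean time on treatment at common horizons: 6 months, and 12 months where the data support it. Keep the strata by sex and age and the 60- and 90-day gap rules.

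**Tables 1, 6 and 29.** Keep them as they are, labelled as observed within unequal follow-up and not to be compared as durations across phases.

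**Cost.** Analysis wording and table shells change; no new data are needed, and the survival approach is already specified for Table 26. The DUS1 version of Table 7 would have to be re-run, since section 6.1 shows that phase completed in four databases by January 2015. Upper quartiles, and possibly the median, may not be reached in DUS2, and the 12-month horizon will rest on the few users who start early in 2014.

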### **9.7.2 Characterisation of Users at the Start Date**

Analysis Tables 8 and 24: Comorbidity at the start date. Users of cilostazol will be characterised according to the presence of comorbidity at any time before the start date. Comorbidity will be assessed for each disease/condition detailed in Table 4 (Section 9.3.3). The number and percentage of users with comorbidity at the start date will be calculated by sex and age group (< 70 years, ≥ 70 years). The distribution of users by socioeconomic indicators will be calculated (Analysis Table 24).

Analysis Table 9: Comedications at the start date. Users of cilostazol will be characterised according to the use of other medications within 6 months before the start date. Comedications to be assessed are those listed in Table 5 (Section 9.3.3). The number and percentage of users treated with other medications at the start date will be calculated by sex and age group (< 70 years, ≥ 70 years).

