Drug dictionary codes/ therapeutic classification	ATC	ATC	ATC	Multilex/British National Formulary	ATC
Clinical indication	Not specifically recorded but based on proxies	Not specifically recorded but based on proxies	Not specifically recorded but based on proxies	Associated with new courses of medications, but completeness is variable Computerised free-text information is available for review	Not specifically recorded but based on proxies
Primary care diagnosis	Yes	Yes	Yes Since January 2004	Yes	No. Diagnoses from outpatient hospital clinics are available
Hospital diagnosis	Yes	Yes (CMBD-AH)	Yes	Recorded by GPs	Yes
Recorded by primary care physicians	No	No	No	Yes	No
Available from hospital database or hospital claims	Yes CMBD-AH	Yes CMBD-AH	Yes	Partial linkage to HES	Yes

Database and Size of Population Size of the Country					
Feature	IACS, Aragón, Spain (N = 1,346,293) a	SIDIAP, Catalonia, Spain (N = 7,565,603) b	German Pharmacoepidemiological Research Database (GePaRD) (N = 81,751,602) c	THIN, United Kingdom (N = 62,435,709) c	Swedish Prescription and Inpatient National Databases (N = 9,415,570) c
Disease and procedure codes	Primary health care: ICPC Hospital: ICD-9	ICD-10-CM	ICD-10-GM	Read codes	ICD-10-CM
Lifestyle risk factors	No	Yes	No	Yes	No
Data availability	Partial since 2005; Complete since 2010	Since 2006	Since 2004	Since 1980	Since July 2005
Approximate time lag (updates)	1 year	1 year	1.5 years	6 months	2012 data will be available in 3-4Q 2013
Approval process for database research	Data application and ethics committee approval required	Data application and ethics committee approval required	Approvals by SHI and Health Ministry are required	Ethics or scientific approval is required	Data application and ethics committee approval required

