### **9.7.5 Assessment of Changes to the Summary of Product Characteristics**

Analysis Tables 17, 18, and 26: The number and percentage of users by sex and age group (< 70 years, ≥ 70 years) will be calculated for the following conditions:

- Smoking: current, past, non-smoker (Analysis Table 17A)
- Number and percentage of users with at least one visit for any reason with a general practitioner or specialist between (a) 2 months and 4 months after the start date and (b) 1 month and 6 months after the start date, evaluated by the clinical review of a sample of patient profiles (Analysis Table 17B) and by diagnosis codes in all users (Analysis Table 17C). Analysis is restricted to patients who are current users of cilostazol at 3 months after the start date.
- Number and percentage of users with at least one visit for intermittent claudication with a general practitioner or specialist between (a) 2 months and 4 months after the start date and (b) 1 month and 6 months after the start date, evaluated by the clinical review of a sample of patient profiles (Analysis Table 17B) and by diagnosis codes in all users (Analysis Table 17C). Analysis is restricted to patients who are current users of cilostazol at 3 months after the start date.
- Discontinuation of cilostazol between 3 months and 4 months after the start date, evaluated using Kaplan-Meier survival curves (Analysis Table 17A and 26)

- Diagnosis within 6 months before the start date: unstable angina, myocardial infarction, or coronary intervention (Analysis Table 17A)
- Concurrent use of cilostazol and two or more platelet aggregation inhibitors (Analysis Table 17A)
- Reduction of daily dose of cilostazol from 200 mg to 100 mg among concurrent users of cilostazol and (a) potentially interacting medications (Analysis Table 18A) or (b) potent inhibitors of CYP3A4 or CYP2C19 (Analysis Table 18B) during continuous use of cilostazol

Analysis Table 19: Rates of visits to general practitioners and/or specialists among users at increased risk of serious cardiac events (patients with history of arrhythmias, coronary heart disease, or hypotension). Rates of visits per 100 person-years and 95% confidence intervals (CI) will be calculated for these patients and for those who are not considered at increased risk of serious cardiac events. Rate ratios and 95% CIs will be estimated comparing the rates in patients with increased risk with rates in patients without increased risk.

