### **9.7.6 Assessment of Contraindications**

Analysis Table 20: Contraindications for cilostazol currently listed in the SmPC will be assessed at the start date according to the following time frames:

- Diagnosis recorded at any time before the start date: renal failure, liver disease, congestive heart failure, diabetic retinopathy, arrhythmias
- Diagnosis recorded within 6 months before the start date: active peptic ulcer, recent cerebral haemorrhage

The number and percentage of patients with contraindications will be calculated by sex and age group (< 70 years, ≥ 70 years).

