### **9.7.7 Overall Assessment of Contraindications**

Analysis Table 28. Number and percentage of users with new 2013 SmPC contraindications and contraindications labelled before 2013.

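### All-history look-back for comorbidity and for five labelled contraindications is longer in DUS2 than in DUS1, which biases their DUS1-DUS2 comparison upward in DUS2

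*Protocol*

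**What the plan says.** Protocol section 9.2.6 sets the general rule: "comorbidity will be assessed for the entire period of data availability before the start date". Section 9.7.2 repeats it for Analysis Table 8: "Users of cilostazol will be characterised according to the presence of comorbidity at any time before the start date".

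Section 9.7.6 (Analysis Table 20) splits the labelled contraindications by window. Five are open-ended: "Diagnosis recorded at any time before the start date: renal failure, liver disease, congestive heart failure, diabetic retinopathy, arrhythmias". Two are not: "Diagnosis recorded within 6 months before the start date: active peptic ulcer, recent cerebral haemorrhage".

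The diagnoses behind the new 2013 contraindications are also bounded in section 9.7.5: "Diagnosis within 6 months before the start date: unstable angina, myocardial infarction, or coronary intervention". Section 9.7.7 then brings both sets together in Analysis Table 28: "Number and percentage of users with new 2013 SmPC contraindications and contraindications labelled before 2013".

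The risk groups for the visit rates in Analysis Table 19 (history of arrhythmias, hypotension or coronary heart disease) are likewise defined over all time before the start date (section 9.3.6).

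Section 9.3.6 says that DUS2 results will be compared with DUS1 to evaluate the risk minimisation measures, and section 7 says that both phases use the same protocol. Table 9 gives the start of data by database; for IACS it reads "Partial since 2005; Complete since 2010".

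**The concern.** An open look-back measures two things at once: whether the patient has the condition, and how long the database has been able to record it. Data start on a fixed calendar date and DUS2 starters come years later, so the second component grows between phases for reasons unrelated to prescribing. The same patients, prescribed to in the same way, would show more recorded renal failure, liver disease, heart failure, diabetic retinopathy and arrhythmia in 2014 than in the DUS1 period.

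What is at stake is how the between-phase contrast is read in Tables 8, 20 and 28. The bias runs against the measures, so a genuine reduction in contraindicated prescribing could look smaller, vanish or appear as an increase. In Table 19 a longer look-back moves patients into the at-risk group. That changes who is being compared, but the documents do not allow the direction of the effect on the rate ratio to be derived. Section 9.7 does not equalise the look-back and section 9.9 does not list it as a limitation.

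**Working it through.** **Plan's own figure.** The protocol gives no figure for look-back. Its only precision statement is Table 11. Exact binomial limits for 10% of 4,000 users reproduce its entry of 9.1% to 11.0%; this serves as a yardstick below.

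**Step 1: maximum available history.** Look-back = start date minus first data date. DUS1 start dates come from Table 2 and DUS2 start dates are the calendar year 2014 (section 9.2.2.1). First data dates come from Table 9. Where the text of section 9.4.2 gives an earlier date (SIDIAP primary care 2000, Swedish inpatient register 1987), both are shown. The 6-month enrolment rule sets the floor.

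| Database, data from | DUS1, years | DUS2, years |
|---|---|---|
| IACS, 2010 (complete) | 0.5-2.0 | 4-5 |
| IACS, 2005 (partial) | 5-7 | 9-10 |
| SIDIAP, 2006 | 3.4-6.3 | 8-9 |
| SIDIAP, 2000 | 9.4-12.3 | 14-15 |
| GePaRD, 2004 | 3-8 | 10-11 |
| THIN, 1980 | 22.4-33 | 34-35 |
| Sweden, July 2005 | 2.8-6.5 | 8.5-9.5 |
| Sweden, 1987 | 21-25 | 27-28 |

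The difference between midpoints is 3.2 to 6.8 years, and DUS2 has the longer history in every row.

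**Step 2: effect on detection.** Assumption: a condition already present is coded at random r times a year, with r = 0.25, 0.5 or 1, and start dates are spread evenly, so look-back is uniform on (a, b). The share detected is

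1 - [exp(-ra) - exp(-rb)] / [r(b - a)].

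For IACS from 2010 with r = 0.25:
- DUS1: 1 - (0.8825 - 0.6065)/(0.25 × 1.5) = 26%.
- DUS2: 1 - (0.3679 - 0.2865)/(0.25 × 1) = 67%.
- Ratio: 0.6745/0.2641 = 2.55. With unchanged prescribing the recorded percentage would be 2.55 times as high in DUS2. A true relative fall of 1 - 1/2.55 = 61% would show as no change.

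Artefactual DUS2/DUS1 ratio for all rows:

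| Database, data from | r = 0.25 | r = 0.5 | r = 1 |
|---|---|---|---|
| IACS, 2010 | 2.55 | 1.98 | 1.44 |
| IACS, 2005 | 1.17 | 1.05 | 1.00 |
| SIDIAP, 2006 | 1.26 | 1.09 | 1.01 |
| SIDIAP, 2000 | 1.04 | 1.00 | 1.00 |
| GePaRD, 2004 | 1.27 | 1.08 | 1.01 |
| THIN, 1980 | 1.00 | 1.00 | 1.00 |
| Sweden, July 2005 | 1.33 | 1.12 | 1.02 |
| Sweden, 1987 | 1.00 | 1.00 | 1.00 |

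**Step 3: sensitivity to the model.** If a first record instead accrues at an assumed constant 1% to 5% a year, detection is 1 - exp(-rate × look-back). The ratios are then larger: 3.3-3.5 (IACS from 2010), 1.5-1.6 (IACS from 2005), 1.6-1.7 (SIDIAP from 2006), 1.2-1.3 (SIDIAP from 2000), 1.7-1.9 (GePaRD), 1.8-1.9 (Sweden from July 2005), and 1.1-1.2 in THIN and in Sweden from 1987.

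**Step 4: yardstick.** Section 9.4.2 puts the participating GePaRD insurers at about 4,000 users. A condition recorded in 10% of DUS1 users would read 10 × 1.27 = 12.7% in DUS2 at r = 0.25, outside the Table 11 interval of 9.1% to 11.0%. At r = 0.5 it would read 10.8%, inside it.

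**Step 5: the windows side by side.** Section 9.1 says that conditions used to evaluate the label-change measures, naming contraindications and also warnings and precautions, are assessed over the 6 months before the start date. Section 9.3.6 uses all time for the warnings group, and section 9.7.6 uses all time for five labelled contraindications. The abstract lists the retained contraindications under the same evaluation. These statements cannot all stand.

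**The case against.** The strongest reply is that the direct measures of the label change are largely protected. Table 7 lists what section 9.3.6 says will be evaluated: new contraindications, antiplatelet combinations, smoking, visits, discontinuation and dose. None of these is an all-history prevalence. The labelled contraindications were retained rather than changed and are described as an additional evaluation, and Table 8 is baseline description. This stands and limits the reach of the point. It does not remove it, because section 9.3.6 compares the phases without exempting these tables and Table 28 mixes the two kinds of window.

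A second reply is that the look-backs are database maxima. Individual history depends on enrolment, which the documents do not give beyond the 6-month minimum. This also stands: the actual gap could be smaller.

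A third is that the label defines some conditions by history, so a 6-month window would miss relevant cases. That is a fair argument for keeping the all-history figures and against making 6 months the only analysis.

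A reader might infer more than the documents support:
- *That contraindicated use will appear to rise in DUS2.* The bias is upward, but a true fall may exceed it; the net result could be a rise, no change or a smaller fall.
- *That every labelled contraindication is affected.* Active peptic ulcer and recent cerebral haemorrhage have a 6-month window.
- *That the effect is large everywhere.* It depends on the database and on which data start date applies.
- *That a planned comparison between databases is distorted.* Results are compiled in a cumulative report (section 6.1), and no formal cross-database contrast is stated.

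**Conclusion.** The concern holds in this bounded form. Table 8 and the five all-time conditions in Table 20, carried into Table 28, are biased upward in DUS2 relative to DUS1 because more history is available; the Table 19 risk groups are defined unequally for the same reason. The direction follows from the protocol's own dates in all five databases.

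The size rests on assumed coding rates. At 0.25 to 1 per year it could be large in IACS if only complete data count and small if the partial data from 2005 contribute fully, with the truth probably between. It is modest in GePaRD and in SIDIAP from 2006, and about nil in THIN and in Sweden from 1987. Under the slower-accrual assumption of 1% to 5% a year no database is wholly free of it. The documents give no observed prevalences, so no corrected percentage can be computed. The 6-month items are unaffected. The conflict between sections 9.1, 9.3.6 and 9.7.6 over the window needs resolving whatever the size of the bias.

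**What to change.** 1. For the DUS1-DUS2 contrast in Tables 8, 20 and 28, and for the Table 19 risk-group definition, add an analysis with the same fixed look-back in both phases within each database. Six months is guaranteed for everyone by section 9.2.4. A longer common window, such as 12 months, could be used among those enrolled that long; Analysis Table 1A already counts users with less than 12 months' enrolment, so the loss can be shown.
2. State that between-phase conclusions rest on this analysis. Keep the all-history figures as description, with the median look-back per phase and database beside them.
3. Reconcile the window in section 9.1 with sections 9.3.6 and 9.7.6, and add unequal look-back to the limitations in section 9.9.

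Cost: one date limit in existing code and an extra column per table. It also means rerunning DUS1, which section 6.1 reports as already completed in THIN, IACS, SIDIAP and Sweden by January 2015. A fixed window is less sensitive to old chronic diagnoses, but its length is the same in both phases, so the gap in available history no longer enters the contrast.
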